9.2 Subject Consent/Assent

When the subject or parent/legal guardian calls the toll free number ([name]) of the Impavido Higher-Weight Patient Registry Coordinating Center, a trained staff member will summarize information on the goals, eligibility requirements, and procedures of the registry. This information will also be on the website.

If on the telephone the patient or parent/legal guardian expresses a tentative desire to participate in the registry, the patient or parent/legal guardian will be mailed paper copies of the goals, eligibility requirements, and procedures of the registry, the Patient Information Sheet/Consent Form/Assent Form (“Consent Form/Assent Form”), and the Release of Medical Information by the Patient’s Physician (“Medical Information Form”).

Consent and assent will be in effect when the patient (or, for adolescents aged 12-17 years, the patient plus the parent/guardian) signs the Consent/Assent Form and the Medical Information Form and mails them back to the Impavido Higher-Weight Patient Registry Coordinating Center.

9.3 Screening Procedures

Physician will complete data form sections relevant to demographics, history of leishmaniasis, history of Impavido treatment (if any), pre-treatment clinical laboratory tests [aspartate aminotransferase (AST), creatinine, and if the patient has VL WBC, hemoglobin, and platelet count], concomitant diseases, concomitant medications.

From this information, eligibility to participate in the Higher-Weight Patient Registry will be determined.

9.4 Outcomes

The Impavido Higher-Weight Patient Registry Coordinating Center will contact the patient's physician at the end of the treatment period, and at 1, 3, and 6 months after the end of therapy, and request that the relevant data forms be completed and submitted.

10 DATA TO BE OBTAINED

10.1 Screening

Demographic Data

Age
Weight
Sex
Race
Prior medications
Geographic area where *Leishmania* infection was acquired
Immune status [normal vs abnormal. If latter, specify disease]

Leishmaniasis History

Site of infection [mark body chart]
Disease parameters
VL : Spleen size
Hemoglobin, platelets, white cell count
ML: Symptoms, Physical status at site of infection
CL : Lesion characteristics at entrance: ulcer, nodule, plaque, scab
Lesion size at entrance: Approximate size [length x width in inches, cm, or finger widths]

Clinical Laboratory Tests

AST, creatinine, and if the patient has VL WBC, hemoglobin, and platelet count

Concomitant Diseases

Concomitant Medications

10.2 Treatment Data

Miltefosine Treatment Regimen

Daily dose in mg, dose in mg/kg, duration of therapy

Adverse events

Symptoms: gastrointestinal, other
Laboratory parameters (if available)

10.3 Efficacy Data at 1, 3, and 6 months

- VL : Spleen size
Hemoglobin, platelets, white cell count
- ML: Symptoms, physical status at original site of infection
- CL : Lesion characteristics: ulcer, nodule, plaque, scab
Lesion size: Approximate size [length x width in inches, cm, or fingerwidths]

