CL generally presents as a papule that enlarges to a nodule and if it ulcerates, does so over 1 to 3 months. CL lesions are often located at exposed areas of the skin (face, arms, legs), either as single or as multiple lesions. Lesions can develop in anybody who intrudes into an endemic region and gets bitten by an infected sand fly. In recent years, industrialized nations have become more aware to the problem due to increasing numbers of imported cases either by military personnel or travelers. In the New World from the Texas-Mexico border down through South America to the level of the Tropic of Capricorn, ulcerative lesions are most common. In the Old World (the Mediterranean, North and Sahelian Africa, the Middle East, the Indian subcontinent, and Central Asia), most lesions are papules, nodules, or nodule-ulcers. The primary species causing CL are diverse: *L. mexicana*, *L. amazonensis*, *L. viannia (v) panamensis*, *L. (v) braziliensis*, *L. (v) peruviana*, and *L. (v) guyanensis* in the New World and *L. major*, *L. tropica*, *L. aethiopica*, and *L. infantum* in the Old World.

[figure not shown]
Mucosal disease (ML) in the New World may result from dissemination of cutaneous organisms (particularly *Leishmania* species of the subgenus *Vianna*: *L. (v). braziliensis*, *L.(v). guyanensis* and *L.(v) panamensis*) to the nares, nasal septum, palate, pharynx, and larynx. Mucosal disease causes a progressive destruction of the mucosa, the cartilage and bones of nose and pharynx, leading to a severe mutilation of the face. ML can be lethal by aspiration pneumonia or other

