11.3 General Analytical Procedures

Descriptive statistics will be used to present study data. Continuous variables will be presented as number of observations (n), mean, standard deviation (SD), median, minimum and maximum values. Categorical variables will be presented as counts and percentages.

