11.6 Analysis of Outcomes

By-subject and summaries of the outcome data will be provided.

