13.2 Data Collection and Monitoring

Data forms will be collected by mail from the patient and/or from the patient's physician. Upon receipt at the Impavido Higher-Weight Registry Coordinating Center, data forms will be stored in a secure controlled access location.

The patient and/or the patient's physician will be responsible for the accuracy of the data.

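### CL lesion size may be recorded in finger widths, and follow-up neither identifies the lesion nor offers a healed state, so CL change cannot be reliably compared between contacts or patients

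*Protocol*

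**What the plan says.** Section 10.1 (Screening) asks for "Lesion size at entrance: Approximate size [length x width in inches, cm, or finger widths", and for the location of disease as "Site of infection [mark body chart". Section 10.3 (efficacy at 1, 3 and 6 months) has two CL items: "CL : Lesion characteristics: ulcer, nodule, plaque, scab" and "Lesion size: Approximate size [length x width in inches, cm, or fingerwidths". There is no lesion number, lesion count, body chart or healed category among the 10.3 items. The ML item in the same list does refer back to the site first infected; the CL items have no such anchor.

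Section 4.1 describes CL lesions as occurring "either as single or as multiple lesions", without a frequency.

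On who reports, section 9.4 has the Coordinating Center ask the physician for the outcome forms, while section 13.2 states that "Data forms will be collected by mail from the patient and/or from the patient's physician". Section 13.3 provides for review before data entry and for queries on incomplete or inaccurate data.

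On analysis, section 11.3 gives a general rule: "Continuous variables will be presented as number of observations (n), mean, standard deviation (SD), median, minimum and maximum values". Section 11.6 adds that "By-subject and summaries of the outcome data will be provided". Neither section mentions lesion size or units.

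**The concern.** The registry's scientific purpose (section 4.4) is to inform the relation between lower mg/kg doses and efficacy, and section 4.2.5 leaves open whether cure rates in heavier US patients are low in absolute terms. For CL, everything the registry can say rests on the two items in 10.3.

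Both are weak as specified. Size may be given in a unit that depends on whose finger is used. Neither size nor type is tied to a lesion marked at screening, so two successive entries for one patient need not describe the same lesion. With no healed category among the listed types, a closed lesion has no listed entry. It would have to be inferred from a zero or blank size, and a blank may also mean that nothing was assessed.

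These are faults in what is collected. A later analysis plan can convert inches or define a responder. It cannot recover the length of an unknown finger or find out which lesion was looked at.

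**Working it through.** The plan states no figure on this point, so there is nothing to reproduce. The check is unit arithmetic.

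**Inputs**
- Permitted units: inches, cm, finger widths (sections 10.1 and 10.3).
- 1 inch = 2.54 cm exactly.
- Finger width f: not defined in the Protocol. Assumed 1.5 to 2.0 cm.
- Enrolment: 3 to 10 patients per year for 5 years (section 3).

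**Step 1: which units convert.** A 1 x 1 inch lesion is 2.54^2 = 6.45 cm2, with no ambiguity. A 1 x 1 finger-width lesion is f^2, between 1.5^2 = 2.25 and 2.0^2 = 4.0 cm2. A 2 x 2 finger-width lesion is 4f^2, between 9 and 16 cm2. The ratio is (2.0/1.5)^2 = 1.78. If the upper limit is 2.25 cm, the ratio is (2.25/1.5)^2 = 2.25. Only finger widths are irrecoverable.

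**Step 2: apparent change in an unchanged lesion when the finger differs.** Take a lesion of 3 x 3 cm = 9 cm2 at both contacts.
- With a 1.5 cm finger it reads 2 x 2 = 4 square finger widths.
- With a 2.0 cm finger it reads 1.5 x 1.5 = 2.25 square finger widths.
- Narrow finger first, wide finger second: 2.25/4 - 1 = -44%.
- Wide finger first, narrow finger second: 4/2.25 - 1 = +78%.

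Rounding to whole finger widths is ignored.

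**Step 3: apparent change when the unit switches.** Suppose the screening entry is 2 x 2 finger widths and a later entry is 9 cm2, measured in cm. The screening area was anywhere from 9 to 16 cm2, so the change lies between 9/9 - 1 = 0% and 9/16 - 1 = -44%. No second assessor is needed for this.

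**Step 4: when the problem cancels.** If the same finger is used at both contacts on the same lesion, f^2 cancels from the ratio and relative change is usable, apart from coarse rounding. Absolute size, and comparison with another patient, still carry the 1.78-fold uncertainty.

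**Step 5: how many records matter.** Expected enrolment is 3 x 5 = 15 to 10 x 5 = 50 patients over VL, CL and ML together. The CL subset is smaller, so a few unusable entries can move its summary.

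**Step 6: several lesions.** Section 4.1 allows multiple lesions, and 10.3 does not say whether one, the largest or all are assessed. An entry may therefore describe a healed lesion while another is active, or the reverse. The Protocol gives neither the number of lesions nor a scoring rule, so no size or direction can be calculated.

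**The case against.** The strongest defence is feasibility. This is a voluntary, descriptive registry that relies on community physicians, and flexible units may be deliberate. By-subject data will be shown, so readers could see units as recorded. Section 9.4 sends outcome requests to the physician, so one assessor may often supply the whole series. The data form itself is not shown and may have room for several lesions; the body chart can take several marks. These points reduce how often the problem will bite. They do not remove it: a finger-width entry is permitted, so nothing in section 13.3 calls for querying it, and a listing shows only what was recorded.

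Three stronger readings are tempting, and the documents do not support them.

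- *Mixed units will be averaged.* Section 11.3 is a general rule that never names lesion size. Nothing says that values are pooled without conversion or that lesions are averaged within a patient, and inches convert exactly. Mixing is a risk, not a stated procedure.
- *Patients often have several lesions.* Section 4.1 says single or multiple. Its word for frequency concerns exposed skin as the location, not the number of lesions.
- *CL efficacy will be overstated.* A reader might compare an 80% chance that one lesion heals with 0.8^3 = 51% for all of three. That assumes independent healing, three lesions, and scoring of one lesion chosen without regard to activity. Lesions in one patient share species, dose and immune status; if they heal together, the gap is zero. A physician who reports the worst lesion would not inflate success. The Protocol defines neither a scoring rule nor a healed status.

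**Conclusion.** The point holds as a defect of data collection. Sections 10.1 and 10.3 permit a unit that cannot be converted to cm, and the 10.3 items neither identify the lesion followed nor provide a healed state, although section 4.1 recognises multiple lesions. Size change cannot be reliably compared between contacts or patients even if the Protocol is followed exactly.

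The distortion from -44% to +78% rests on the assumed finger width of 1.5 to 2.0 cm and on different fingers being used at the two contacts. It does not apply to the relative change of one lesion measured throughout with the same finger. For patients with several lesions, the recorded status may not represent all of them, and the direction of any bias is unknown. The change should be made: the items concerned are the only CL efficacy data, and the remedy is cheap.

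**What to change.** - In sections 10.1 and 10.3, require CL lesion length x width in cm only.
- Number each lesion on the body chart already marked at screening.
- At each contact, record type (with healed added to the list) and size for every numbered lesion, and note any new lesion.
- In section 11.6, state that CL outcome is summarised per patient across all recorded lesions. The detailed rule may sit in the statistical analysis plan, provided the lesion-level data are collected.

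The cost is a form change, a ruler, and slightly more writing for physicians of patients with several lesions. If a CL success rate is reported, it may be lower than one based on a single lesion. Nothing in treatment or in the visit schedule changes.

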11 ANALYTICAL PLAN

11.1 Sample Size

Since there is no hypothesis for this study, there is no formal sample size calculation.

11.2 Analytical Populations

Data for all eligible subjects will be analyzed. An eligible subject is anyone who received at least one administration of Impavido for leishmaniasis.

11.3 General Analytical Procedures

Descriptive statistics will be used to present study data. Continuous variables will be presented as number of observations (n), mean, standard deviation (SD), median, minimum and maximum values. Categorical variables will be presented as counts and percentages.

11.4 Analysis of Baseline Data

By-subject and summaries of the baseline data will be provided.

11.5 Analysis of Treatment Compliance Data

By subject and summaries of compliance with prescribed treatments will be provided, including total exposure (number of days, total dose in mg, daily dose in mg/kg) to Impavido.

11.6 Analysis of Outcomes

By-subject and summaries of the outcome data will be provided.

12 ADMINISTRATIVE AND REGULATORY STANDARDS

This protocol will be submitted to IND# 105,430. The Principal Investigator (PI) will sign a Form FDA 1572.

12.1 Ethical Review of Protocol

The PI will obtain protocol approval from a central IRB before starting the study.

12.2 Informed Consent

Subject consent will be obtained in accord with protocol section 9.2

12.3 Responsibility for Subject Care

The patient's physician is responsible for the care of his/her subject.

12.4 Treatment Cost

The patient is responsible for the cost of treatment including miltefosine.

13 STUDY DOCUMENTATION/DATA MANAGEMENT

13.1 Subject Identification (ID) Code

Each subject will be assigned a subject ID code. The Subject ID code will be used on all data forms and reports of the data to the IRB and FDA.

13.2 Data Collection and Monitoring

Data forms will be collected by mail from the patient and/or from the patient's physician. Upon receipt at the Impavido Higher-Weight Registry Coordinating Center, data forms will be stored in a secure controlled access location.

The patient and/or the patient's physician will be responsible for the accuracy of the data.

13.3 Data Editing and Control

Data received at the Impavido Higher-Weight Patient Registry Coordinating Center will be reviewed prior to being entered into the main study database. If incomplete or inaccurate data are found, a data clarification request will be forwarded to the patient and/or patient's physician for a response.

13.4 Data Analysis

An analysis of all data will be performed at the intervals specified by 2127-4.

A final clinical study report will be prepared in accordance with International Committee on Harmonization E3 Structure and Content of Final Clinical Study Reports.

13.5 Publication

The results of the full study may be published at the discretion of the sponsor. No personal identifying data will be available in any external communication or publication.

13.6 Subject Confidentiality

To maintain subject confidentiality, all electronic records and data reports using the subject ID code. Data forms and other records containing the patient's name, address, and telephone number will be stored in a secure location and only the protocol staff will have access to the records.

14 ROLES AND RESPONSIBILITIES OF STUDY PERSONNEL

14.1 Principal Investigator

Signs the protocol agreement, below, and the Form FDA 1572. The PI is responsible for passage of the protocol and any amendments through a "central" IRB before starting the study. The PI is responsible for interaction with the Impavido Higher-Weight Patient Registry Coordinating Center to ensure protocol adherence, data integrity, and overall coordination of the study.

14.2 Subinvestigators

Subinvestigators are responsible for performing the PI's duties in his/her absence. In all sections of this protocol, "PI" is taken to mean "PI or subinvestigator in the absence of the PI".

14.3 Higher-Weight Patient Registry Coordinating Center

The Impavido Higher-Weight Registry Coordinating Center maintains and staff's personnel who respond to calls from patients and enrolled subjects. It also prepares and provides data forms; designs, develops, and validates the clinical trial database; performs data entry into the clinical trial database and performs database quality control and data analysis.

